Behavioral Sleep Interventions: A recent systematic review and meta-analysis found behavioral treatments for young, typically developing children (birth to 5 years) with sleep disturbances result in significant improvements in sleep-onset latency, night waking frequency, and night waking duration.⁶⁵ However, there is currently very low-quality evidence for behavioral treatments in adolescents, as well as children/adolescents with NDDs.⁶⁵ A few studies have shown that interventions predominantly aimed at parent education in pediatric sleep hygiene improve sleep disturbances in young children with NDDs,⁶⁶⁻⁷¹ as well as older children and adolescents with DDs.⁷² Currently, behavioral sleep interventions for children with NDDs are sparse and limited by methodological concerns (e.g. small sample sizes, wide age ranges, & lack of objective measures).^{6,12,65,73} To our knowledge, no studies have reported behavioral sleep interventions specific to adolescents with NDDs. Behavioral interventions and exogenous melatonin show promise in treating sleep problems in adolescents with NDDs.⁷⁴

CHARACTERISTICS OF THE SUBJECT POPULATION

4. Accrual

Is this study conducted solely at sites under the oversight of the Joint Pediatric IRB (e.g. UNMC, TNMC, CH&MC, UNO)?

Yes

A. What is the total number of subjects (per group, as applicable) needed to complete the research in order to achieve the scientific objectives of the research?

A convenience sample of 40 adolescents diagnosed with ASD and/or ADHD and 40 parents (or legal guardians) of adolescents (1 parent per adolescent) will be recruited through the UNMC MMI, all MMI outreach clinics, CHMC, and CHMC clinics. A focused plan will be in place to oversample females (e.g. clinicians and study team will be encouraged to invite non-white and female adolescents to participate), given the approximate 4:1 male to female ratio of NDDs. Our anticipated ratio is 3:1 male to female participants. Adolescents and their parent will be identified by a doctoral-prepared nurse as meeting the inclusion criteria.

B. What is the statistical or other justification for the total number of subjects needed to complete the research in order to achieve the scientific objectives of the research?
The sample of 40 was chosen following a sample size calculator, specific to pilot SMARTs,⁷⁵ assuming 85% probability, an estimated early non-response rate of 50%, and a minimum of 3 participants falling into the non-responder groups.

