C. Based on the anticipated number of screen failures and/or subject withdrawals, what is the maximum number of subjects that will need to be consented in order to achieve the scientific objectives of the research?

The maximum number of adolescent study participants with ASD and/or ADHD that will be consented is 40. In addition, a maximum of 40 parents of the adolescent participants will also be consented, for a total maximum number of 80 participants. [name] (PI) will meet participants in-person at baseline, week 4, and week 8. In addition, endogenous melatonin samples will be collected from participants by the end of the first week of baseline data collection. [name] will conduct weekly telephone check-ins to discuss daily adherence to the Bedtime Bank (e.g consistent bedtimes and tracker completion) and wearing the actigraph. Technical problems will be triaged quickly and may result in additional telephone calls or in home visits when necessary to further help with participant retention. Participants will also be compensated for their time.

5. Gender of the Subjects

A. Are there any enrollment restrictions based on gender?

No

6. Age Range of Subjects

A. What is the justification for inclusion of children in this research?

Adolescents (10-18 years of age) with neurodevelopmental disorders (NDDs) are included in this study. Adolescents with NDDs are vulnerable to sleep disturbances, and there is a critical need for evidence-based sleep interventions that target this population. The PI, mentoring team, and staff at the facilities in which the participants will be recruited all have expertise in accommodating for adolescents with NDDs. The proposed study will pilot a sequential, multiple assignment, randomized trial (SMART) design utilizing exogenous melatonin, The Bedtime Bank, and their combination for the management of sleep disturbance in adolescents with NDDs. Knowledge gained from this study will contribute to future full-scale SMARTs and our long-term goal of developing evidence-based guidelines for sleep interventions for children and adolescents currently experiencing or at-risk for sleep disturbances.

B. What is the age range for the child subjects, and what is the justification for selecting this age range?

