metabolite in urine, correlates well with the total level of melatonin in the blood during the collection period.⁸⁵ At baseline, adolescents and parent(s) will be given the urine collection kit and instructed on how to collect the adolescents urine (first morning void and evening), including written instructions (Appendix L) and a mock return demonstration. The pre-labeled and de-identified urine samples will be collected from participants by responsible personnel prior to the implementation of the first stage intervention. Specimens will then be stored in a locked and secured freezer (at the UNMC Biospecimen Bank) until they can be run by the UNMC Biospecimen Bank staff for analysis. Urinary creatinine will also be measured as melatonin sulfate is referenced as ng/mg creatinine to control for dilution of urine. Urine samples will only be used for the study described in the consent form.

3. Actigraphy: Objective measure of sleep patterns based on the correlation between sleep-wake state and motor activity. Adolescents wear the Actiwatch Spectrum (Philips Respironics, Bend, OR) on their wrist for 7-days (24 hrs/day) to establish baseline sleep patterns, as well as for 4 weeks (24 hrs/day) for the first stage treatment. TST will be used as the primary tailoring variable to determine responder status. A minimum of 4 weekday nights (Mon-Thurs) and 1 weekend (Fri-Sat) night is required. Participants will be provided with information regarding the care and use of the Actiwatch (Appendix M).
4. Sleep Diary: During the time adolescents are wearing the actigraph, adolescents will record an approximate time of sleep and wake to aid in data analyses.⁸⁶ Participants will also be asked to write down any times the device is removed, prolonged quiet activities, and atypical sleep (Appendix C). Reliability in completing the diaries will be established via weekly telephone checks by the study's investigators.
5. MEMs Button: Medication adherence will be monitored using MEMs Buttons. This button is attached to the melatonin bottle. When a dose is administered, the adolescent or parent will press the button to record the dose. Data from the MEMs Button will be downloaded from the device to a computer to ensure dose fidelity.
6. First Stage Treatment (see **Figure 2**): Adolescents will be randomly assigned to 4 weeks melatonin OR 4 weeks of *The Bedtime Bank*. Randomization will follow the real-time randomization for SMART designs.⁷⁵

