WEEK 4: Second Stage Treatment Decision (see **Figure 2 & Table 1**)

1. Abbreviated Acceptability Rating Profile (AARP): A parent-completed form to measure overall satisfaction with the treatment protocol (Appendix D). Research has found that the AARP possesses acceptable internal consistency, reliability, and validity.⁸⁷ The modified AARP includes 8 items regarding treatment acceptability rated on a Likert-type scale (1 = strongly disagree to 6 = strongly agree). Parents are asked whether they agree that the intervention was acceptable and effective, whether they would keep using it and recommend it to others, and whether they felt it was a good way to solve their child's sleep problems. The AARP yields a total

score that ranges from 8-48, with a score above the midpoint (28+) indicating minimal treatment acceptability.

2. Parent(s) repeat PROMIS sleep measures.
3. Adolescents repeat sleep questionnaires (CASQ and PROMIS sleep measures).
4. Parent(s) and adolescent complete semi-structured interview to discuss treatment acceptability (Appendix E). Semi-structured interviews will be audio recorded for later transcription.
5. Actigraphy: Data will be downloaded and analyzed (automated algorithm Respiromics Actiware 6, Philips Respiromics, Bend, OR) to determine responders from non-responders to determine Second Stage Treatment Decision. **Responder** = ≥ 18 minute nightly increase in TST.
6. MEMs Button: Data will be dowloaded and analyzed to assess medication adherence.
7. Second Stage Treatment (see **Figure 2**): Participants who respond remain on the assigned treatment. Participants who are nonresponsive are re-randomized to a different treatment option. Participants who do not complete the assigned treatment remain on the assigned treatment or withdraw from the study. Randomization will occur based on responder status and will follow the real-time randomization for SMART designs.⁷⁵ Adolescents will wear the actigraph on their wrist for an additional 4 weeks (24 hrs/day) for a study total of 9 weeks.

WEEK 8: Study Conclusion

1. Parent(s) complete AARP and PROMIS, adolescents repeat sleep questionnaires (CASQ and PROMIS), and parent(s) and adolescent complete semi-structured interview to discuss treatment acceptability. Semi-structured interviews will be audio recorded for later transcription.
2. Actigraphy Data will be downloaded and analyzed to determine response status.

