3. MEMs Button: Data will be dowloaded and analyzed to assess medication adherence.

Interventions

1. Melatonin (liquid, immediate release, 3 mg) 30 minutes before bedtime (Appendix N).⁵⁸ Reported dosages of melatonin have ranged from 0.75 mg to 15 mg.⁵ A 3 mg dose was chosen as Malow et al. found the greatest satisfactory dose response at 3mg.⁷⁹
2. *The Bedtime Bank* protocol (Appendix F).
3. Melatonin+ *The Bedtime Bank* (or The Bedtime Bank+ Melatonin) is a potential treatment option for the Second Stage Treatment Decision (see **Figure 2**).

C. Identify all procedures, interventions, evaluations and tests that are

1) Performed solely for research purposes.

All procedures described above will be performed solely for research purposes.

2) Performed more frequently than they would be if the subject was not participating in the research.

All procedures described above will be performed solely for research purposes.

3) Performed on the subjects in the course of their normal clinical care (i.e. for diagnostic or treatment purposes) where the data are used for research.

N/A

D. Does this research involve genetic testing?

No

E. Will any un-used human biological material (HBM) be used to create a tissue bank for future research?

No

F. Describe briefly the statistical methods used to analyze the data.

Data will be analyzed by the PI, an on-site statistician, and consultants with expertise in SMARTs, with a portion of the PIs training plan devoted to analysis of SMARTs. The pilot will address feasibility (e.g. recruitment/retention, protocol adherence, suitability of primary tailoring variable, other potential tailoring variables, protocol fidelity, and missing data) and acceptability (AARP and semi-structured interview) to prepare the PI for a full-scale SMART.⁷⁵ Pilot SMARTs provide preliminary knowledge about the direction of the effect,⁷⁵ and the aims focus on preliminary knowledge; however, conducting formal tests of outcomes or effect size estimation is not justified.⁷⁵ We cannot statistically control for age, sex, and race in a pilot SMART, however in the subsequent full-scale SMART, outcomes will be assessed using regression techniques described by Almirall et al.,⁸⁸ which will control for age, race, and sex.

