Descriptive Statistics: Statistical analyses will be performed using SPSS version 25.0 (IBM Corp., Armonk, NY). Descriptive statistical analyses (mean, median, standard deviation, frequency, and range) will be used to describe demographics, questionnaires (CASQ, PROMIS, & AARP), and *The Bedtime Bank* tracker.

Response: Actigraphy data will be downloaded to a computer and TST will be calculated using an automated algorithm (Respironics Actiware 6, Philips Respironics, Bend, OR) to determine response status of ≥ 18 minute nightly increase in TST.

For Aim 1 & 2: Analysis of these aims will be the proportion of treatment responders within each subgroup.

For Aim 3: Salimetrics laboratory (Carlsbad, CA) will perform DLMO analysis and provide the PI with results, including baseline melatonin concentration (pg/mL). The relationship of baseline melatonin and response rate to the melatonin-only, as well as treatment acceptability (AARP & interview) will be assessed.

G. Indicate the study design/phase by checking the appropriate box(s).

- Phase I
- Phase I/II
- Phase II
- Phase II/III
- Phase III
- Phase IV
 - ♦ Other: Sequential, multiple assignment, randomized trial
- Case-Control
- Cohort
- Cross-sectional
- Randomized, parallel group
- Randomized, cross-over
- Placebo-Controlled
- Single Blind
- Double Blind
- Triple Blind

DRUGS, BIOLOGIC DRUGS AND DEVICES

13. Drugs and Biologic Drugs

A. Does this study involve an investigational drug or biologic drug?

Yes

B. Does this research involve an FDA-approved and marketed drug or biologic drug?

No

14. Devices

A. Does this research involve an investigational device?

No

B. Does this research involve an FDA-approved and marketed device?

No

CONFIDENTIALITY AND PRIVACY

15. Confidentiality and Privacy

A. Will research data be stored:

- 1) On a secure server at UNMC/TNMC/CH&MC/UNO?

Yes

2) On a local hard drive?

No

3) On a portable computer?

Yes

a) Is the portable computer encrypted and password protected?

Yes

4) On a flash drive?

No

5) In a database accessible through the internet?

No

6) In hard copy?

Yes

a) Will the hard copies be stored at UNMC/TNMC/CH&MC/UNO during the conduct of the study (i.e. not the long term storage location)?

Yes

b) Will the hard copies be stored off campus during the conduct of the study (i.e. not the long term storage location)?

No

c) Describe the physical methods to protect the hard copies (e.g. locked file cabinet or locked briefcase).

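### Does the justification for 40 adolescents fail because Section 4.B leaves out the number of non-responder groups, the allocation rule and the expected loss?

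*Combined protocol and SAP*

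**What the plan says.** Section 4.B bases the sample of 40 on a calculator for pilot SMARTs, "assuming 85% probability, an estimated early non-response rate of 50%, and a minimum of 3 participants falling into the non-responder groups". It gives no number of groups and no loss rate.

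The form's question at 4.C reads "Based on the anticipated number of screen failures and/or subject withdrawals, what is the maximum number of subjects that will need to be consented". The answer is "The maximum number of adolescent study participants with ASD and/or ADHD that will be consented is 40", the same number that 4.A gives for recruitment.

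On allocation, Section 12.B (Baseline, item 6) says "Randomization will follow the real-time randomization for SMART designs". The Week 4 text (item 7) cites the same method and adds that the second randomisation depends on responder status. The reference is the one cited for the calculator. At week 4, "Participants who are nonresponsive are re-randomized to a different treatment option", while "Participants who do not complete the assigned treatment remain on the assigned treatment or withdraw from the study". Under Interventions, item 3, melatonin plus The Bedtime Bank "is a potential treatment option for the Second Stage Treatment Decision".

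Section 12.F says of Aims 1 and 2: "Analysis of these aims will be the proportion of treatment responders within each subgroup". It also states that formal outcome tests and effect-size estimation are not justified in this pilot.

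**The concern.** With no formal tests, the cell-size criterion is the only numerical basis for 40, so it should be possible to check it. Section 12.B lists three interventions and sends non-responders to a different one by randomisation. That suggests two options in each first-stage arm, and so four non-responder cells. If second-stage allocation is simple, the chance that every cell reaches 3 falls well below 85%.

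Loss adds to the worry. Adolescents who do not complete the first treatment are not re-randomised, so they fill no cell. The number to be recruited and the maximum to be consented are both 40, which leaves no visible allowance.

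At stake is Aim 2: a responder proportion in a cell of 0 to 2 adolescents says very little.

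**Working it through.** **Inputs**
- From 4.B: N = 40, target 0.85, non-response q = 0.5, minimum 3 per group.
- From 12.B: two first-stage arms; the ratio is not stated, so I assume 20 and 20.
- Assumed, because not stated (Figure 2 is not shown): the number of cells, whether the 85% is joint, the second-stage rule, and the loss.

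**The plan's own figure.** The smallest N that reaches 85% is:
- 34 with four cells, joint criterion, equal arms and an even second-stage split;
- 37 with the same but a simple first stage;
- 49 with four cells, joint criterion, equal arms and a simple second stage;
- 19 with two groups (20 if N must be even).

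None of these is 40. An allowance of 15% would give it, since 34/(1 − 0.15) = 40, but no such rate is stated. The figure is neither confirmed nor contradicted.

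**Four cells, joint criterion, even split.** Each arm needs at least 6 non-responders. P(Bin(20, 0.5) ≥ 6) = 1 − 21,700/1,048,576 = 0.9793. Both arms: 0.9793² = **0.959**. Permuted blocks of 4 within arm give 0.935.

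**Four cells, joint criterion, simple re-randomisation.** Per arm, sum over k of P(Bin(20, 0.5) = k) × P(3 ≤ Bin(k, 0.5) ≤ k − 3) = 0.8202. Both arms: 0.8202² = **0.673**.

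**Four cells, per-cell criterion, simple re-randomisation.** Each cell is Bin(20, 0.5 × 0.5) = Bin(20, 0.25). P(≥ 3) = 1 − (0.0032 + 0.0211 + 0.0669) = **0.909**.

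**Two groups, joint criterion.** P(Bin(20, 0.5) ≥ 3)² = 0.9998² = **0.9996**.

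**Loss before week 4**, taken as random at rate L (four cells, joint, even split): P(Bin(20, 0.5(1 − L)) ≥ 6)².

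| Loss | Probability |
|---|---|
| 0% | 0.959 |
| 10% | 0.892 |
| 15% | 0.837 |
| 20% | 0.765 |

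The value crosses 0.85 at L = 0.140. If the loss leaves exactly 17 per arm (34 in all), the figure is 0.9283² = 0.862.

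**How short the cells fall in the adverse case** (four cells, simple re-randomisation, no loss). The chance that some cell is below 3 is 1 − 0.673 = 0.327. The chance that some cell is below 2 is 1 − 0.905 = 0.095. The chance that some cell is empty is 1 − 0.987 = 0.013. Most of the shortfall is a cell of 2 instead of 3.

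**The case for a change.** The best argument for a change runs as follows. Four cells is the natural reading, because re-randomising needs at least two options and the combination is described as only one possibility. With two groups about 20 adolescents would suffice, which makes 40 hard to explain. A joint criterion is also the more natural meaning of a minimum across the groups. On that reading the chance of at least one cell below 3 is 4% or 33%, depending on a rule the documents do not spell out, and one sentence would settle it.

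Much of this stands. The paragraph cannot be reproduced, four cells is the likelier reading, and a loss rate is missing. Two things weaken it:
- The documents do name an allocation method, by citation and from the same source as the calculator. That method may already balance; these documents do not show whether it does. If it balances, stating its rule changes nothing in the trial.
- The 85% is not said to be joint. Read per cell, 40 passes even under simple allocation.

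The point about loss is weaker than it looks. The wording about completing the research belongs to the form's question in 4.A; the answer speaks of recruiting 40, which agrees with 4.C. Section 4.C also describes weekly calls, home visits and compensation to support retention. Retention and missing data are themselves feasibility results under 12.F.

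**Conclusion.** No change follows. The 67% is correct arithmetic but requires four cells, a joint 85% and simple re-randomisation all at once, and none of these is established. Changing any one of them, with no loss, restores the criterion: 96% with an even split (94% with blocks of 4), 91% per cell, over 99.9% with two groups. Under balanced four-cell re-randomisation 40 also absorbs just under 14% random loss.

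These figures assume 20 per arm, 50% non-response and loss unrelated to response. They are sensitive to the second of these: with an even split and no loss, 40% non-response gives 76%. That is uncertainty about the stated assumption, which a pilot exists to reduce.

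The consequence of a small cell is limited. Section 12.F reports proportions descriptively, and a proportion from 3 adolescents is little better than one from 2. Section 4.B would read better with the group count, the meaning of the 85% and the assumed loss written down. That would document the calculation; nothing here shows that following the plan as written gives a wrong result.

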Risk for completing questionnaires: There is the potential for psychological risk in that the adolescent and the adolescent participants parents will be asked to identify concerns and answer questions regarding the adolescents sleep characteristics that may make the person feel uncomfortable. However, this risk should be no greater than the discomfort parents are normally exposed to due to their adolescents sleep-related problems. Questionnaires were pilot tested and required 7-10 minutes to complete. At each visit, it is estimated it will take the participant about 7-10 minutes to complete the questionnaires. We have private consultation rooms in the clinics that will be used by participants during completion of the questionnaires, and the participants can take breaks if needed.

Risk for wearing research device: Generally, the risk of wearing research devices is minimal. There is no contraindication to wearing an actigraph. It is possible that participants may find the actigraph uncomfortable to wear. If the research participants feel uncomfortable wearing the research device, they have the right to withdraw from the research at any time.

Risk for sleep interventions:

The Bedtime Bank: In a feasibility study (181-16-EP), the UNMC IRB deemed our behavioral sleep intervention, The Bedtime Bank, minimal risk. There is the potential for psychological risk in that the adolescent and the adolescent participants parents will be asked to track the adolescents' sleep characteristics that may make the person feel uncomfortable.

Melatonin: Generally, the risk of administering 3 mg of melatonin, 30 minutes before bedtime is minimal. A recent review of twenty clinical studies that used exogenous melatonin found that most studies specifically reported that exogenous melatonin was not associated with any side effects.^{8,60} Although of low incidence, side effects of melatonin in children may include: daytime sleepiness, headaches, dizziness, increased enuresis,

irritability, abdominal pain, and diarrhea.^{8,60}

17. Risk Classification

What is the overall risk classification of the research?

♦ Minimal risk

Greater than minimal risk

Significant risk

18. Minimization of Risk

A. Will the research utilize procedures already being performed on the subjects for diagnostic or treatment purposes?

No

B. Describe how the subjects of the research will be monitored by the investigators and other research personnel to ensure their safety.

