Monitoring study safety will occur from the initial screening, throughout the informed consent process, and through study completion. Weekly monitoring of participants (telephone check-in) and internal monthly quality audits of protocol fidelity will occur. Any adverse events will be reviewed in real time according to University policy. Follow-up visits to analyze and discuss treatment acceptability will be scheduled every four weeks throughout the eight-week study, for a total of three visits. During this time, any stress or discomfort encountered as a result of the study will be discussed. The PI and study coordinators will also be available to the study participants via phone or email should the participants or their parents have any questions or concerns regarding the study.

C. Describe the process by which the PI will be informed and how the PI, in turn, will inform other research staff about events concerning subject safety (including (a) interim results; (b) adverse events; (c) unanticipated problems involving risks to subjects or others; (d) noncompliance; (e) complaints).

1) At UNMC/TNMC/CH&MC and/or UNO (check all that apply).

Not applicable. The PI is the only person listed in Section I of the IRB Application.

♦ By email or campus mail (for events which do not constitute immediate subject safety hazards)

♦ By phone

♦ By in-person meeting

By scheduled submission of case report forms

Other. Explain.

2) At external study sites under the oversight of the Joint Pediatric IRB as applicable

(check all that apply).

By email or mail (for events which do not constitute immediate subject safety hazards)

By phone

By in-person meeting or teleconference

By scheduled submission of case report forms

♦ Other. Explain. N/A

D. Describe the auditing plan for research conducted:

1) Within the Organization (UNMC, TNMC, UNO or CH&MC), identify who will conduct the audits and specify the audit frequency.

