Prior to the accrual of human subjects, a detailed data and safety monitoring plan will be submitted to the UNMC IRB and to the funding agency for approval (See final DSMP plan dated 12/31/18). The monitoring of compliance for the proposed procedure will be done by the UNMC IRB, the mentoring team (Drs. [name], [name], [name], and [name]), and a Data Safety Monitoring Board (DSMB). UNMC has two standing DSMBs. One is for any cancer related study, and one is for non-cancer studies. The non-cancer DSMB includes several members experienced with clinical research and clinical trials, including biostatistics expertise and a research subject advocate. The principal investigator [name] has identified a content expert ([name]) for this DSMB who is independent of the study team. The PI will provide written reports of progress and compliance every 6 months to the DSMB. The DSMB will set up meetings and prepare minutes and responses to the study team for the duration of the study. Each report will include monitoring of: compliance with informed consent and eligibility requirements, recruitment plan according to protocol, follow-up data collection according to protocol, expected and actual accrual, protocol violations, and patient withdrawals from the study. Adverse events encountered by the research team will be reported to the PI immediately. Per University policy, all serious adverse events (AE) will be reported to the UNMC IRB within two business days after the PI is notified of the AE. Any fatal adverse events will be reported immediately according to institutional policies. Results of the monitors reports will be provided in writing to the PI and discussed as needed within 1 month (or less if the situation requires). All deviations from protocol and adverse events will be reviewed by the PI, co-investigators, and senior nurse scientists to identify if follow-up action is need (e.g., protocol tightening or consequent IRB changes).

2) At external study sites under the oversight of the Joint Pediatric IRB, identify who will conduct the audits and specify the audit frequency.

N/A

E. Is there is an independent DSMB for this study?

Yes

Will you be submitting the DSMB charter?

Yes

F. Describe the specific criteria by which the investigator would withdraw individual subjects from the research (for example, medical criteria, such as specific toxicity or lack of efficacy or non-medical criteria, such as non-compliance).

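### Six of the seven melatonin side effects listed in section 16 have no structured, arm-identical elicitation and no planned summary in the protocol as provided

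*Combined protocol and SAP*

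**What the plan says.** Section 16 (Melatonin) states that "side effects of melatonin in children may include: daytime sleepiness, headaches, dizziness, increased enuresis", and goes on to irritability, abdominal pain and diarrhoea. It describes these as uncommon.

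Section 18.B describes how safety is monitored. "Weekly monitoring of participants (telephone check-in) and internal monthly quality audits of protocol fidelity will occur". "Follow-up visits to analyze and discuss treatment acceptability will be scheduled every four weeks throughout the eight-week study", and about those visits it adds: "During this time, any stress or discomfort encountered as a result of the study will be discussed".

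Section 4.C gives the content of the weekly calls as adherence to The Bedtime Bank and wearing of the actigraph. Section 12.B (Sleep Diary) adds a check that diaries are being completed. Neither mentions symptoms.

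Table 1 in section 12.B has no adverse-event item. It does schedule the CASQ and the PROMIS sleep measures at baseline, week 4 and week 8.

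Section 12.F covers feasibility, acceptability, descriptive statistics for the questionnaires and the proportion of responders. It has no adverse-event summary.

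Section 18.D.1 says: "Adverse events encountered by the research team will be reported to the PI immediately". Its list of contents for the six-monthly DSMB reports does not name adverse events. It refers to a separate data and safety monitoring plan (DSMP), which is not among the documents provided.

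**The concern.** The protocol says which effects it expects from melatonin, but for six of the seven it describes no routine question about them. The prompt it does describe has two weaknesses. It is open, so the answer depends on what the family thinks worth raising. It also asks only about discomfort caused by the study, so the family must judge cause before reporting.

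That judgement can differ by arm. No blinding box is marked in section 12.G, and families know whether they were given a supplement or a behavioural programme. The same headache may be reported by a family on melatonin and passed over by a family on The Bedtime Bank. It is also plausible, though the documents do not say so, that an adolescent will not raise enuresis with a parent present, and that irritability will be put down to ASD or ADHD.

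Without a baseline question, a symptom recorded at week 4 cannot be classed as new, worse or long-standing.

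The trial exists to prepare a full-scale SMART by assessing feasibility and acceptability, and tolerability bears on acceptability. Section 18.G also makes termination depend on participants appearing to be at risk, which requires that harms be seen.

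**Working it through.** **Step 1. Coverage of the listed effects.**

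| Effect (section 16) | Asked at baseline | Asked later in the same way in every arm | Summary in 12.F |
|---|---|---|---|
| Daytime sleepiness | Yes (CASQ, PROMIS) | Yes, weeks 4 and 8 | Yes, as questionnaire scores |
| Headache, dizziness, enuresis, irritability, abdominal pain, diarrhoea | None described | Open prompt only, tied to cause | None |

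So 7 − 1 = 6 effects lack structured collection.

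**Step 2. Number exposed.** Section 4.B: "The sample of 40 was chosen following a sample size calculator, specific to pilot SMARTs". The calculator's inputs are 85% probability, 50% early non-response and at least 3 in the non-responder groups. If this means 3 in each of two second-stage options per arm with balanced re-randomisation, at least 6 non-responders are needed per arm. Then P(X ≥ 6 | n = 17, 0.5)² = 0.862, so 34 adolescents would be enough. With unrestricted re-randomisation, 50 would be needed. The exact rule is not given and Figure 2 is not shown, so 40 can be neither confirmed nor called wrong. This point does not depend on it. Taking 40 as planned, and assuming 1:1 allocation (the ratio is not stated), 40 / 2 = 20 start on melatonin.

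**Step 3. Chance of recording no case.** With true rate p and share captured c, P(no case) = (1 − p·c)^20. The documents give no event or capture rates, so both are assumed.

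| p | c = 1 | c = 0.5 | Difference |
|---|---|---|---|
| 10% | 0.90^20 = 0.122 | 0.95^20 = 0.358 | 24 points |
| 5% | 0.95^20 = 0.358 | 0.975^20 = 0.603 | 24 points |
| 2% | 0.98^20 = 0.668 | 0.99^20 = 0.818 | 15 points |

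**Step 4. Unequal capture.** If the true rate is p in both arms and capture is c_M on melatonin and c_B on The Bedtime Bank, the expected recorded risk ratio is (p·c_M)/(p·c_B) = c_M/c_B. With assumed capture of 50% and 25% it is 0.50/0.25 = 2.0, when the truth is 1.0.

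**Step 5. What full capture would give.** With 20 per arm, Fisher's exact test (two-sided 0.05) has 17% power for 20% v 5% and 45% for 30% v 5%. No case in 20 leaves a one-sided 95% upper limit of 1 − 0.05^(1/20) = 13.9%. Better elicitation improves the counts, but a formal comparison stays out of reach.

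**The case against.** The strongest reply is that harms are not left to chance. Visits include a topic that staff raise. Weekly calls are named as monitoring. There are recorded interviews at weeks 4 and 8. Daytime sleepiness is already measured in both arms from baseline. This stands. A reader might infer that adverse effects are captured only when volunteered or noticed, and the text does not support that. The sentence in 18.D.1 about events the team encounters is a rule for onward reporting and does not say how events are found.

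Second, the DSMP, the DSMB charter and the interview guide (Appendix E) were not available, and any of them might specify an adverse-event procedure. This also stands. A reader might infer that harms will certainly be under-counted. The documents support only that they are likely to be, if the described procedures are all there is.

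Third, comparing harms is not one of the three aims, and section 12.F says formal tests of outcomes are not justified in this pilot. A reader might infer that poor elicitation is what makes the arms impossible to compare. That is too strong. Sleepiness can be compared descriptively, and for the other six the sample size would limit any comparison however the data were collected.

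Finally, naming symptoms every week may itself prompt reports. That is a real cost of the fix. The same checklist in all arms limits it but does not remove it.

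None of this supplies a symptom question, a baseline or a table for the six effects.

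**Conclusion.** The point holds for six of the seven listed effects. As described, the plan collects them through an open prompt tied to perceived cause, with no baseline and no planned summary. They are likely to be under-recorded, possibly to a different degree by arm, and new onset cannot be separated from symptoms already present.

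Under the assumptions above (20 on melatonin, half of cases captured), the chance of recording no case rises from 12% to 36% at a true rate of 10%, and from 67% to 82% at 2%. These figures illustrate the size of the problem and do not estimate it. They describe a single arm. The risk ratio of 2.0 in step 4 shows how unequal capture could mislead, again on assumed rates.

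This does not threaten the response aims. It is a cheap improvement worth making before enrolment, conditional on what the DSMP and Appendix E contain.

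**What to change.** - **Section 12.B and Table 1:** add a fixed checklist of the six effects, asked once in the baseline week and at each weekly call already planned. Use the same wording in every arm and ask whatever the family thinks the cause is.
- **Section 12.F:** add one descriptive table of new or worse symptoms by current treatment, with no formal test. Show the first-stage weeks separately, because second-stage treatment depends on response.
- **Section 18.D.1:** add adverse events to the contents of the DSMB reports.
- **If the DSMP or Appendix E already specifies this:** cite it in 12.B and 12.F instead.

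The cost is one or two minutes per call. With one baseline contact and eight weekly calls that is 9 × 1 to 9 × 2, or about 9 to 18 minutes per family over the trial. There will be more non-serious events to log, and some risk of suggestion from naming symptoms. No new visit is needed and no treatment rule changes.
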